13. STUDY MEDICATION EXPOSURE

Patients in this study will have been prescribed a NOAC treatment for their NVAf.

Prescription of the treatments will have been done under the sole responsibility of the healthcare professional and before considering the participation in the study.

14. OUTCOMES

14.1 Primary Outcome

The primary outcome is the pattern of usage of non-vitamin K oral anticoagulants (NOACs) prescribed according to their Summary of Product Characteristics (SmPC), based on the percentage of patients by NOAC type and dose the patient is taking at the time of the study visit. Timeframe to complete data collection for this outcome is one day, the study visit day.

Document:	H:\HOR-Europe\2019\2512352 - Study on anticoagulation management - BI\Proyecto\Estadistica\SAP\S		
	AP_REBELD_version1.0_08072020.docx		
Author:	██████████	Version Number:	Version 1.0
		Version Date:	[08072020]

Template No.: RWI_TP_BIOS0013 Revision 1

Reference: RWI_WI_BIOS0015

Effective Date: 15Jun2018

Table 4. Primary variable collected at the time of the study visit

Variable	Obtained from medical records
Current NOAC active substance and dose	x

14.1.1 Primary Analysis of Primary Outcome

The primary outcome analysis will be performed for the FAS. For the primary objective, the pattern of usage of NOAC will be described as the percentage of patients by NOAC type and dose.

The pattern of NOAC usage will be also analyzed descriptively by the following subgroups, if a minimum of 50 patients have been included in the required subgroups:

- Sex (female, male)
- Age at the time of the study visit (75-79, 80-84, ≥ 85 years)
- Comorbidities at the time of the study visit: heart failure, coronary artery disease, peripheral vascular disease, diabetes, chronic kidney disease, liver disease and cancer.

14.2 Secondary Outcomes

14.2.1 Patient's characteristics

Patient's characteristics at the time of the study visit by the NOAC type that the patient is taking at the time of the study visit. Patients will be also stratified by the duration since the

Document: H:\HOR-Europe\2019\2512352 - Study on anticoagulation management - BI\Proyecto\Estadistica\SAP\S
AP_REBELD_version1.0_08072020.docx

Author: [REDACTED] Version Number: Version 1.0
Version Date: [08072020]

Template No.: RWI_TP_BIOS0013 Revision 1

Reference: RWI_WI_BIOS0015

Effective Date: 15Jun2018

first NOAC initiation date until the study visit date (>4 months / ≤ 4 months) (See Patient's characteristics: refer to Section 11, Table 3.).

14.2.2 OAC treatment management

OAC treatment management (since first NOAC initiation until the study visit date), based on the following variables:

- Previous vitamin K antagonist (VKA) treatment (yes/no), VKA treatment duration in years
- Duration since NVAF diagnosis until first NOAC initiation,
- Duration of first NOAC treatment (first NOAC active substance, start and stop date, first NOAC dose and its dose changes),
- Switch to new NOAC (active substance, start/stop date, dose and dose changes, reason for switch to new NOAC): number of patients that switch their first or further NOAC and mean number of switches.
- Total time in NOAC treatment
- History and current antiplatelet treatment (yes/no, start date, end date, active substance).

Patients will be also stratified by the duration since the first NOAC initiation date until the study visit date (> 4 months / ≤ 4 months).

14.2.3 Clinical Frailty Scale

Clinical Frailty Scale grading at the time of the study visit, by current NOAC type.

Document:	H:\HOR-Europe\2019\2512352 - Study on anticoagulation management - BI\Proyecto\Estadistica\SAP\S		
	AP_REBELD_version1.0_08072020.docx		
Author:		Version Number:	Version 1.0
		Version Date:	[08072020]

Template No.: RWI_TP_BIOS0013 Revision 1

Reference: RWI_WI_BIOS0015

Effective Date: 15Jun2018

14.2.4 Prevention strategy

The first NOAC usage by NOAC type, for primary prevention or secondary prevention, at the time of first NOAC initiation.

14.3 Analysis of Secondary Outcomes

All analysis of secondary outcomes will be performed for the FAS.

14.3.1 Patient's characteristics

Patient's characteristics at the time of the study visit will be summarized descriptively by current NOAC type. Patients will be also stratified by duration since the first NOAC initiation until the study visit date (>4 months / ≤ 4 months). All covariates related to patient's characteristics (refer to Section 11 , Table 3.) will be analyzed descriptively by NOAC type and by the duration since the first NOAC initiation. Standardized differences between Pradaxa® and other NOACs will be estimated for these covariates. For this, a minimum of 50 patients is required for each group.

14.3.2 OAC treatment management

For OAC treatment management, descriptive analysis of previous VKA treatment (yes/no), VKA treatment duration in years, first NOAC treatment duration, first NOAC dose and dose changes, new NOAC treatment duration, new NOAC dose and dose changes. Duration since NVAF diagnosis until first NOAC initiation and total time in NOAC treatment will be described. Also, the reason for switches, the number of patients that switched their first or further NOAC and mean number of switches will be presented. Antiplatelet use will be also summarized.

Document:	H:\HOR-Europe\2019\2512352 - Study on anticoagulation management - BI\Proyecto\Estadistica\SAP\SAP_REBELD_version1.0_08072020.docx		
Author:	██████████	Version Number:	Version 1.0
		Version Date:	[08072020]

Template No.: RWI_TP_BIOS0013 Revision 1

Reference: RWI_WI_BIOS0015

Effective Date: 15Jun2018

The subgroup analysis of these outcomes by the duration since the first NOAC initiation until the study visit date (> 4 months / ≤ 4 months) will also be performed. For this subgroup analysis, a minimum of 50 patients is required for each group.

14.3.3 Clinical Frailty Scale

Clinical Frailty Scale grading at the time of the study visit by current NOAC type will be described as the number of patients on each category of frailty as evaluated by the investigator according to patient's records. In addition, CFS score will be summarized in the following two categories: Frailty patients (CFS scoring >4) and Non-frailty patients (CFS scoring ≤ 4).

14.3.4 Prevention strategy

[figure not shown]
First NOAC usage will be described by NOAC type, for primary prevention or secondary prevention, at the time of first NOAC initiation.

Document: H:\HOR-Europe\2019\2512352 - Study on anticoagulation management - BI\Proyecto\Estadística\SAP\SAP_REBELD_version1.0_08072020.docx
Author: [REDACTED] Version Number: Version 1.0
Version Date: [08072020]

Template No.: RWI_TP_BIOS0013 Revision 1

Reference: RWI_WI_BIOS0015

Effective Date: 15Jun2018

Document: H:\HOR-Europe\2019\2512352 - Study on anticoagulation management - BI\Proyecto\Estadistica\SAP\S
AP_REBELD_version1.0_08072020.docx

Author: [Redacted]

Version Number: Version 1.0

Version Date: [08072020]

Template No.: RWI_TP_BIOS0013 Revision 1

Reference: RWI_WI_BIOS0015

Effective Date: 15Jun2018

14.6 Exploratory analysis

History and current antiplatelet treatment will be described by current NOAC type.

Treatment received at the time of thromboembolic and bleeding events will be described, including NOAC, VKA and antiplatelet treatments.

Doses of current NOAC treatment received by the patient will be described according to HAS-BLED score (as low, intermediate and high risk).

The percentage of underdosed and overdosed patients for current NOAC treatment will be described.

HAS-BLED total score (as <3 , $3-5$, ≥ 5) will be described according to NOAC and antiplatelet current treatment.

Multivariate logistic regression will be used to evaluate the association between the Clinical Frailty Scale (dependent variable: Frailty patients - CFS scoring >4 vs Non-frailty patients - CFS scoring ≤ 4) and the thromboembolic and the bleeding events (independent variables). To calculate this analysis, only events that have occurred subsequent to the start of anticoagulant therapy (not those prior to the start of VKA / NOACs) will be considered. Other factors will be age, sex, BMI, smoking habit, alcohol consumption, time since NVAf diagnosis, NVAf type, modified EHRA scale, procedures and interventions, comorbidity Charlson index and clinical risk factors. Univariate analysis will be performed. All variables which have a P value of less than 0.1 will be included in the multivariate analysis.

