7.2.17 Underdosed or overdosed patient (current NOAC treatment)

The recommended dose of dabigatran is 150mg twice a day (BID). Patients who meet any of the following criteria should perform a dose adjustment to 110mg BID, so those who receive the recommended dose of 150mg BID will be classified as overdosed. Those who receive a 110mg BID dose and do not meet any of the following criteria will be classified as underdosed:

- Age ≥ 80 years
- Patients aged 75-79 years and HAS-BLED ≥ 3
- Moderate renal impairment (creatinine clearance 30-50mL/min)

The recommended dose of rivaroxaban is 20mg once a day (QD). Patients who meet the following criteria should perform a dose adjustment to 15mg QD, so those who receive the recommended dose of 20mg QD will be classified as overdosed. Those who receive a 15mg QD dose and do not meet following criteria will be classified as underdosed:

- Moderate renal impairment (creatinine clearance 30-50mL/min) or severe renal impairment (creatinine clearance 15-29mL/min)

The recommended dose of apixaban is 5mg BID. Patients who meet at least 2 of the following 3 criteria should perform a dose adjustment to 2.5mg BID, so those who receive the

Document:	H:\HOR-Europe\2019\2512352 - Study on anticoagulation management - BI\Proyecto\Estadistica\SAP\S		
	AP_REBELD_version1.0_08072020.docx		
Author:		Version Number:	Version 1.0
		Version Date:	[08072020]

Template No.: RWI_TP_BIOS0013 Revision 1

Reference: RWI_WI_BIOS0015

Effective Date: 15Jun2018

recommended dose of 5mg BID will be classified as overdosed. Those who receive a 2.5mg BID dose and do not meet at least 2 of the 3 following criteria will be classified as underdosed:

- Age \geq 80 years
- Body weight \leq 60 kg
- Serum creatinine \geq 1,5 mg/dl or severe renal impairment (creatinine clearance 15-29mL/min)

The recommended dose of edoxaban is 60mg OD. Patients who meet at least 1 of the following 2 criteria should perform a dose adjustment to 30mg OD, so those who receive the recommended dose of 60mg OD will be classified as overdosed. Those who receive a 30mg OD dose and do not meet at least 1 of the 2 following criteria will be classified as underdosed:

- Body weight \leq 60 kg
- Moderate or severe renal impairment (creatinine clearance 15-50mL/min)

A categorical variable for dose category with 3 levels will be described:

- 1) Appropriately dosed
- 2) Underdosed
- 3) Overdosed.

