NOAC	Valid N* No				

Document: H:\HOR-Europe\2019\2512352 - Study on anticoagulation management - BI\Proyecto\Estadística\SAP\SAP_REBELD_version1.0_08072020.docx

Author: [REDACTED] Version Number: Version 1.0
Version Date: [08072020]

Template No.: RWI_TP_BIOS0013 Revision 1

Reference: RWI_WI_BIOS0015

Effective Date: 15Jun2018

		Nasal	Pulmonary	Articular-muscular	Conjunctival
	Yes N missing				
Type of NOAC	Valid N Dabigatran Rivaroxaban Apixaban Edoxaban N missing				
Antiplatelet	Valid N* No Yes N missing				
Type of antiplatelet	Valid N Aspirin Clopidogrel Prasugrel Ticlopidine Ticagrelor Cilostazol Triflusal Dipyridamole Others N missing				

*Number of events in each column

One event could be associated with more than one treatment

Table 50. Current NOAC dose according to HAS-BLED

		HAS-BLED			
		Low risk	Intermediate risk	High risk	Total
Dabigatran dose	Valid N 110mg BID 150mg BID N missing				
Rivaroxaban dose	Valid N				

Document: H:\HOR-Europe\2019\2512352 - Study on anticoagulation management - BI\Proyecto\Estadística\SAP\SAP_REBELD_version1.0_08072020.docx

Author: [REDACTED] Version Number: Version 1.0
Version Date: [08072020]

Template No.: RWI_TP_BIOS0013 Revision 1

Reference: RWI_WI_BIOS0015

Effective Date: 15Jun2018

		HAS-BLED			
		Low risk	Intermediate risk	High risk	Total
	15mg QD 20mg QD N missing				
Apixaban dose	Valid N 2.5mg BID 5mg BID N missing				
Edoxaban dose	Valid N 30mg QD 60mg QD N missing				

Table 51. Overdosing and underdosing of current NOACs

		Appropriately dosed (n,%)	Underdosed (n,%)	Overdosed (n,%)
Dabigatran	Dabigatran (Age <80 years)			NA
	Dabigatran (Age ≥80 years)		NA	
	Dabigatran (75-79 years and HAS-BLED < 3)			NA
	Dabigatran (75-79 years and HAS-BLED ≥ 3)		NA	
	Dabigatran (creatinine clearance >50mL/min)			NA
	Dabigatran (creatinine clearance 30-50mL/min)			NA
Rivaroxaban	Rivaroxaban (creatinine clearance >50mL/min)			NA

Document: H:\HOR-Europe\2019\2512352 - Study on anticoagulation management - BI\Proyecto\Estadística\SAP\S AP_REBELD_version1.0_08072020.docx

Author: [REDACTED] Version Number: Version 1.0
Version Date: [08072020]

Template No.: RWI_TP_BIOS0013 Revision 1

Reference: RWI_WI_BIOS0015

Effective Date: 15Jun2018

		Appropriately dosed (n,%)	Underdosed (n,%)	Overdosed (n,%)
	Rivaroxaban (creatinine clearance ≤ 50 mL/min)		NA	
Apixaban	Apixaban (Age < 80 years)			NA
	Apixaban (Age ≥ 80 years)		NA	
	Apixaban (Body weight > 60 kg)			NA
	Apixaban (Body weight ≤ 60 kg)		NA	

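### The under-/overdosing percentages have no stated denominator, and mock Table 51 splits by single criteria in a way that contradicts the joint rules of SAP 7.2.17

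*SAP*

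**What the plan says.** SAP 14.6 (Exploratory analysis) states: "The percentage of underdosed and overdosed patients for current NOAC treatment will be described". It names neither a denominator nor a comparison between drugs.

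SAP 7.2.17 classifies each user by a drug-specific reduction rule:
- **Dabigatran:** any one of age ≥80; age 75–79 with HAS-BLED ≥3; clearance 30–50 mL/min. "Those who receive a 110mg BID dose and do not meet any of the following criteria will be classified as underdosed".
- **Rivaroxaban:** clearance 15–50. "Those who receive a 15mg QD dose and do not meet following criteria will be classified as underdosed".
- **Apixaban:** at least two of age ≥80; weight ≤60 kg; creatinine ≥1.5 mg/dl or clearance 15–29. The text for the reduced dose reads "BID dose and do not meet at least 2 of the 3 following criteria will be classified as underdosed".
- **Edoxaban:** weight ≤60 kg or clearance 15–50.

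A full dose counts as overdosed when the rule is met. The section ends: "A categorical variable for dose category with 3 levels will be described" (appropriate, under, over), again with no denominator.

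The mock output is Table 51 in SAP 17.4, "Overdosing and underdosing of current NOACs". It has 18 rows, each defined by one criterion of one drug, such as "Dabigatran (75-79 years and HAS-BLED < 3". Every row has one cell marked NA. No row shows all users of a drug, and none shows the joint rule.

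**The concern.** Under 7.2.17 a patient can be underdosed only if the drug's rule is not met, and overdosed only if it is met. The rules select very different shares of a population aged ≥75: age ≥80 alone meets the dabigatran rule, is one of two criteria needed for apixaban, and plays no part for rivaroxaban or edoxaban. A percentage with no stated denominator therefore mixes prescribing with the share of patients in whom the error is possible.

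A programmer who follows Table 51 literally must also leave empty some cells in which 7.2.17 places patients. Section 7 of the protocol cites underdosing in the elderly as part of the study's rationale, so this exploratory table is likely to be read closely.

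**Working it through.** The documents give no figure for these shares or percentages, so there is no plan figure to reproduce.

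**1. NA cells in Table 51 against 7.2.17.** In each row below, the joint rule allows the classification that the table rules out.

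| Table 51 row | Marked NA | Patient whom 7.2.17 classifies there |
|---|---|---|
| Dabigatran, age <80 | Overdosed | Aged 75–79, HAS-BLED ≥3 or clearance 30–50, on 150 mg BID |
| Dabigatran, clearance >50 | Overdosed | Aged ≥80, on 150 mg BID |
| Dabigatran, clearance 30–50 | Overdosed | Anyone in the row on 150 mg BID |
| Apixaban, age ≥80 | Underdosed | No second criterion, on 2.5 mg BID |
| Apixaban, ≤60 kg | Underdosed | No second criterion, on 2.5 mg BID |
| Apixaban, creatinine ≥1.5 or clearance <30 | Underdosed | No second criterion, on 2.5 mg BID |
| Edoxaban, >60 kg | Overdosed | Clearance 15–50, on 60 mg |
| Edoxaban, clearance >50 | Overdosed | ≤60 kg, on 60 mg |

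The same reasoning reaches the overdosed NA cells for dabigatran 75–79 with HAS-BLED <3 (clearance may be 30–50) and for the three remaining apixaban rows (the other two criteria may both be met). The rivaroxaban rows, which rest on a single criterion, agree with 7.2.17 for clearance ≥15.

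**2. Direction, without assuming a case mix.** Take one population aged ≥75 with clearance ≥30. Those who can be underdosed on dabigatran are aged 75–79 with HAS-BLED <3 and clearance >50.
- They all lie inside the rivaroxaban group (clearance >50).
- They all lie inside the apixaban group. Below age 80, two apixaban criteria would require ≤60 kg together with creatinine ≥1.5. Cockcroft-Gault then gives at most (140 − 75) × 60 / (72 × 1.5) = 36.1 mL/min, which is below 50.

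There is no such nesting against edoxaban, because a dabigatran patient in this group may weigh ≤60 kg.

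**3. Size if all users are the denominator.** Let S be the share of users not meeting the rule and q the rate of reduced dosing among them, equal for all drugs. Then underdosed % = q × S, and the ratio between two drugs is the ratio of their S. I simulated age, sex, weight and creatinine, with HAS-BLED independent of them, under four assumed populations with clearance ≥15. Dabigatran users with clearance 15–29 were treated as meeting the rule. All entries except the ratio are percentages.

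| Population | ≥80 y | ≤60 kg | Creat. ≥1.5 | Clearance ≤50 | HAS-BLED ≥3 | S dabi. | S riva. | S apix. | S edox. | Ratio apix./dabi. |
|---|---|---|---|---|---|---|---|---|---|---|
| Younger | 33 | 9 | 3 | 22 | 15 | 47.2 | 78.3 | 95.6 | 74.7 | 2.0 |
| Intermediate | 43 | 12 | 6 | 34 | 25 | 31.5 | 66.5 | 91.4 | 62.8 | 2.9 |
| Base | 47 | 16 | 9 | 43 | 30 | 23.9 | 56.8 | 87.2 | 53.3 | 3.65 |
| Older | 57 | 24 | 15 | 57 | 45 | 12.5 | 43.2 | 76.1 | 39.0 | 6.1 |

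In the base case with q = 20%, all-user underdosing is 0.20 × 23.9 = 4.8% for dabigatran and 0.20 × 87.2 = 17.4% for apixaban. Restricting to clearance ≥30 changes the base ratio only to 3.63. A cruder grid treating the criteria as independent gives 2.1 to 9.7, median 4.2. Overdosing runs the other way: (1 − 0.239)/(1 − 0.872) = 5.95 for dabigatran against apixaban in the base case, 3.7 to 12 across the four populations.

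**4. Size in the rows that Table 51 plans.** Here the row percentage is q × the share of the row not meeting the joint rule. Base case, q = 20%:
- Dabigatran: age <80, 9.1%; 75–79 with HAS-BLED <3, 13.0%; clearance >50, 8.4%.
- Rivaroxaban: clearance >50, 20.0%.
- Apixaban: age <80, 19.6%; >60 kg, 19.0%.
- Edoxaban: >60 kg, 12.6%; clearance >50, 18.8%.

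The rivaroxaban row exceeds the dabigatran rows by 20.0/13.0 = 1.5 to 20.0/8.4 = 2.4. The same comparison gives 20.0/16.5 = 1.2 to 20.0/12.1 = 1.7 in the younger population and 20.0/10.6 = 1.9 to 20.0/5.8 = 3.4 in the older.

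**5. With joint-rule denominators.** Underdosed among those not meeting the rule equals q for every drug, so the ratio is 1.0.

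**The case against.** A reader might infer that the SAP reports each error as a percentage of all users of a drug. It does not say so. A three-level variable invites that reading, but Table 51 has no all-users row and the all-user percentages in step 3 fill none of its cells.

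Several overdosing rows are already sound. Everyone in the rows for dabigatran age ≥80, dabigatran 75–79 with HAS-BLED ≥3, edoxaban ≤60 kg and edoxaban clearance 15–50 meets the rule, as in the rivaroxaban row for clearance ≤50. Equal prescribing gives equal percentages there, so it would be wrong to say that the sponsor's drug must show the most overdosing in the planned table. For underdosing, the apixaban rows quoted in step 4 and the edoxaban clearance >50 row are diluted only slightly; the loss falls on dabigatran and on edoxaban >60 kg.

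The analysis is exploratory and descriptive, and no cross-drug comparison of dosing is announced. The share of all users who are wrongly dosed is also a legitimate prevalence.

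Joint-rule denominators have limits too. Patients not meeting the dabigatran rule are all under 80, while those not meeting the apixaban rule include people of 80 and over, so case mix still differs; section 9.9 of the protocol itself raises channeling. Counts may be small. If 500 patients split equally, 125 per drug, the base case leaves 125 × 0.239 ≈ 30 dabigatran users not meeting the rule and 125 × 0.128 = 16 apixaban users meeting it. Both fall below the 50-patient minimum that SAP 8.5 sets for subgroups. A result of 6/30 has a Clopper-Pearson interval of 7.7% to 38.6%.

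All of this stands. It narrows the point but does not remove the missing denominator or the NA cells that conflict with 7.2.17.

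**Conclusion.** The specification gap is real. The denominator is unstated, and for dabigatran, apixaban and edoxaban Table 51 does not implement the rule in 7.2.17. The contradictory NA cells and the nesting of the dabigatran group within the rivaroxaban and apixaban groups follow from the SAP's own rules and formula, given clearance ≥30 for the nesting.

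The sizes do not come from the documents. The roughly 2- to 6-fold figure applies only to all-user underdosing, only to the extreme pair (apixaban against dabigatran), and assumes the same case mix and error rate for every drug. In the planned table the base-case underdosing gap is about 1.5- to 2.4-fold. A single multiplier, or a claim that the plan compares drugs on dosing quality, would go beyond the text. The primary outcome, NOAC type and dose, is unaffected.

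**What to change.** Reconcile Table 51 with SAP 7.2.17, leaving the dosing rules unchanged; nothing here bears on whether those criteria are clinically right. In SAP 14.6 and Table 51, report for each NOAC:
- (a) n and % of users meeting the joint rule;
- (b) underdosed among users not meeting it;
- (c) overdosed among users meeting it;
- the three-level distribution among all users.

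Give each of (a) to (c) its denominator and a 95% CI. Remove or correct the NA cells that conflict with 7.2.17.

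Add a note that the all-user percentages depend on the share of users meeting each drug's rule and are not comparable across NOACs. The note should add that (b) and (c) remain descriptive, with residual case-mix differences and possibly small denominators.

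The cost is a few table rows, some SAP wording and wider intervals. No new data are needed.

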4.6 Changes to Analysis from Protocol

Per protocol, the variable “reason for VKA switch will be described under the OAC treatment management outcome. Finally, reason for VKA treatment switch has not been collected specifically in the VKA section of the CRF. This has been deleted from section 14.2.2 of SAP.

New analysis not included in the final protocol have been considered:

- Antiplatelet treatment according to current NOAC type
- Treatment received at the moment of thromboembolic and bleeding events.
- For all NOACs, the different doses that patients take according to HAS-BLED score.
- Underdosed and overdosed patients (for current NOAC treatment).
- HAS-BLED total score according to NOAC and antiplatelet current treatment.
- Multivariate model to evaluate the association between the Clinical Frailty Scale (dependent variable) and the thromboembolic and the bleeding events (independent variables). To calculate this analysis, only events that have occurred subsequent to the start of anticoagulant therapy (not those prior to the start of VKA / NOACs) will be considered. Univariate analysis will be performed. All variables which have a P value of less than 0.1 will be included in the multivariate analysis.

Document:	H:\HOR-Europe\2019\2512352 - Study on anticoagulation management - BI\Proyecto\Estadistica\SAP\S		
	AP_REBELD_version1.0_08072020.docx		
Author:	██████████	Version Number:	Version 1.0
		Version Date:	[08072020]

Template No.: RWI_TP_BIOS0013 Revision 1

Reference: RWI_WI_BIOS0015

Effective Date: 15Jun2018

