17.3.3 Secondary outcome: Clinical Frailty Scale

Table 42. Clinical Frailty Scale grading at the time of the study visit according to current NOAC type

		Dabigatran	Rivaroxaban	Apixaban	Edoxaban	Total
CFS score	Valid N					
	1-Very fit					
	2-Well					
	3-Managing well					
	4-Vulnerable					
	5-Mildly frail					
	6-Moderately frail					
	7-Severely frail					
	8-Very severely frail					
	9-Terminally ill					
	N missing					
CFS (categorized)	Valid N					
	Non-frailty patients (CFS scoring ≤4)					
	Frailty patients (CFS scoring >4)					
	N missing					

Document: H:\HOR-Europe\2019\2512352 - Study on anticoagulation management - BI\Proyecto\Estadistica\SAP\S AP_REBELD_version1.0_08072020.docx

Author: [REDACTED] Version Number: Version 1.0
Version Date: [08072020]

Template No.: RWI_TP_BIOS0013 Revision 1

Reference: RWI_WI_BIOS0015

[figure not shown]
Effective Date: 15Jun2018

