	Apixaban (Serum creatinine $< 1,5$ mg/dl or creatinine clearance ≥ 30 mL/min)			NA
	Apixaban (Serum creatinine $\geq 1,5$ mg/dl or creatinine clearance < 30 mL/min)		NA	
Edoxaban	Edoxaban (Body weight > 60 kg)			NA
	Edoxaban (Body weight ≤ 60 kg)		NA	
	Edoxaban (creatinine clearance > 50 mL/min)			NA
	Edoxaban (creatinine clearance 15-50 mL/min)		NA	

Table 52. HAS-BLED score according NOAC+antiplatelet current treatment

		HAS-BLED score				
		Valid N	< 3	3-5	≥ 5	N missing
Current treatment	Dabigatran+aspirin					
	Dabigatran+clopidogrel					
	Dabigatran+peasugrel					
	...					
	... (for all combinations)					

Row percentage will be calculated

Document: H:\HOR-Europe\2019\2512352 - Study on anticoagulation management - BI\Proyecto\Estadistica\SAP\S AP_REBELD_version1.0_08072020.docx

Author: [REDACTED]

Version Number:

Version 1.0

Version Date:

[08072020]

Template No.: RWI_TP_BIOS0013 Revision 1

Reference: RWI_WI_BIOS0015

Effective Date: 15Jun2018

Table 53. Multivariate logistic model to evaluate the association between the Clinical Frailty Scale and the thromboembolic and the bleeding events

Variable	Estimate	Standard error	t-value	Pr> t	OR

*dependent variable: CFS in two categories: Frailty patients - CFS scoring >4 vs Non-frailty patients - CFS scoring ≤4)

*independent variables: thromboembolic and bleeding events. Other factors will be age, sex, BMI, smoking habit, alcohol consumption, time since NVAF diagnosis, NVAF type, modified EHRA scale, procedures and interventions, comorbidity Charlson index and clinical risk factors. Univariate analysis will be performed and all variables which have a P value of less than 0.1 will be included in the multivariate analysis.

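### The exploratory frailty regression models the nine-grade Clinical Frailty Scale only as >4 versus ≤4; under assumed inputs this costs about 23–42% of the information at odds ratios of 1.6–2.0, which an added ordinal model would recover

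*SAP*

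**What the plan says.** SAP 14.6 states the aim as follows: "Multivariate logistic regression will be used to evaluate the association between the Clinical Frailty Scale" and thromboembolic and bleeding events, counting only events after the start of VKA or NOAC treatment. The outcome is binary: "dependent variable: Frailty patients - CFS scoring >4 vs Non-frailty patients - CFS scoring ≤ 4". The footnote to mock Table 53 (SAP 17.4) repeats it: "dependent variable: CFS in two categories". Candidate factors enter the multivariable model if their univariate P value is below 0.1.

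The cut is a general derivation in SAP 7.2.14, and protocol 9.7.1 already uses it as an additional descriptive summary. The scale itself has nine grades. Protocol Annex 3 lists them, and SAP Table 42 has a row for each, down to "9-Terminally ill". The full grading has one use: under SAP 14.3.3 it "will be described as the number of patients on each category of frailty", by current NOAC type. No ordinal or continuous analysis of the grade against events is planned.

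**The concern.** A binary outcome treats grades 1 and 4 as the same and grades 5 and 8 as the same, while the step from 4 to 5 carries the whole contrast. If events go with a general shift along the scale, the cut throws away part of that shift, and the odds ratios for the event terms become less precise.

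This is the only regression visible in the documents, and the study plans about 500 patients. The SAP does not say whether the event terms stay in the model whatever their univariate P value. Read literally, the 0.1 screen applies to them too, so lost precision could remove the terms of interest from Table 53. At stake is a real association being reported as absent or too imprecise to use, although the data that would sharpen it are already collected.

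**Working it through.** **The plan's own figure.** The documents give no power or precision for the regression. Their only size figure is the width of the 95% Clopper-Pearson interval at n = 500 (protocol Table 4): 5.46, 7.20, 8.22, 8.76 and 8.94% for prevalences of 10 to 50%. Recomputing gives the same values within 0.01 point. They concern single proportions and say nothing about an odds ratio.

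**Inputs from the documents.** Binary outcome >4 vs ≤4 (SAP 14.6, Table 53); nine grades (protocol Annex 3, SAP Table 42); n about 500 (protocol 9.5, SAP 4.2).

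**Inputs assumed, because the documents give none.** Share of patients with an event q = 0.15; odds ratio (OR) 1.6 or 2.0, the same at every cut-point; two-sided 5% test; no covariates. Three grade distributions (grades 1 to 9, in %) for patients without an event:
- 18% frail: 8, 20, 32, 22, 10, 5, 2, 0.5, 0.5
- 36% frail: 5, 12, 25, 22, 16, 11, 7, 1, 1
- 50% frail: 3, 8, 18, 21, 20, 16, 11, 2, 1

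**Step 1: near OR 1.** With f the frail share and p_k the grade proportions, the information on the log odds ratio is n·q(1−q)·(1−Σp_k³)/3 for the ordinal model and n·q(1−q)·f(1−f) for the cut. The relative efficiency of the cut is 3f(1−f)/(1−Σp_k³):
- 18% frail: 0.4428/0.9469 = 0.47
- 36% frail: 0.6912/0.9661 = 0.72
- 50% frail: 0.7500/0.9709 = 0.77

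The losses are 53%, 28% and 23%.

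**Step 2: at the assumed effects.** Let f0 be the frail share without an event. The frail share with an event is f1 = OR·f0/(1−f0+OR·f0). The binary log odds ratio has variance 1/[nq·f1(1−f1)] + 1/[n(1−q)·f0(1−f0)]. The ordinal variance is the inverse of the expected Fisher information of the cumulative-logit model, with the cut-points profiled out. Power is Φ(ln OR/SE − 1.96).

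Example, 18% frail and OR 2.0: f1 = 0.36/1.18 = 0.305. The binary variance is 1/(75 × 0.305 × 0.695) + 1/(425 × 0.18 × 0.82) = 0.0629 + 0.0159 = 0.0788, so SE = 0.281 and power = Φ(0.693/0.281 − 1.96) = 70%. The ordinal SE is 0.224, so power = 87%. The loss is 1 − (0.224/0.281)² = 36%.

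| Frail share (no event) | OR | SE binary | SE ordinal | Information lost | Power binary | Power ordinal | Gain (points) |
|---|---|---|---|---|---|---|---|
| 18% | 1.6 | 0.292 | 0.223 | 42% | 36.3% | 55.8% | 19.5 |
| 18% | 2.0 | 0.281 | 0.224 | 36% | 69.5% | 87.2% | 17.7 |
| 36% | 1.6 | 0.252 | 0.221 | 23% | 46.1% | 56.6% | 10.5 |
| 36% | 2.0 | 0.252 | 0.222 | 23% | 78.4% | 87.8% | 9.4 |
| 50% | 1.6 | 0.256 | 0.221 | 26% | 44.9% | 56.6% | 11.7 |
| 50% | 2.0 | 0.264 | 0.222 | 29% | 74.9% | 87.7% | 12.8 |

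**Step 3: simulation.** With 3,000 runs per setting (Wald test of the 2×2 log odds ratio against the Wilcoxon test), power for 18, 36 and 50% frail was 70 vs 87%, 79 vs 88% and 75 vs 87% at OR 2.0. At OR 1.6 it was 40 vs 58%, 45 vs 56% and 45 vs 57%. These agree with the table to within about 4 points.

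**Step 4: sensitivity.** Four other assumed distributions (20, 34, 52 and 60% frail; 10 or 20% with an event) lose 22–40% at OR 1.5–2.0. Near OR 1 the loss falls to 14–20% if patients cluster in the grades around the cut and half are frail. It rises to about 70% if only 10% are frail.

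**The case against.** The case for the cut is good. It is a predefined derivation in the SAP, taken from the protocol. It also sits where the scale's own wording changes: in Annex 3, grade 4 is vulnerable but not dependent on others, and grade 5 is the first grade called frail and needs help with important daily activities. The odds of being frail is a sensible and readable target. If the association with events is concentrated at that step, the binary model answers the right question and the efficiency comparison does not apply. Grade 9 is defined by life expectancy below 6 months without other signs of frailty, so the nine grades are not strictly ordered by frailty. The model is exploratory, was added in the SAP, and serves no primary or secondary objective. All of this stands. It limits the point to one of efficiency and is the reason to keep the binary model.

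A reader might infer three stronger things that do not hold:
- **That the cut discards half the information, or costs about 31 points of power (57% vs 88%).** Those figures apply information computed at OR 1 to an odds ratio of 2.0. With 18% frail, the binary information is 9.4 at OR 1 but 12.7 (1/0.0788) at OR 2.0, because the frail share in the event group rises to 30.5%.
- **That SAP 14.6 departs from SAP 4.6.** Section 4.6 names "the Clinical Frailty Scale (dependent variable) and the thromboembolic and the bleeding events (independent variables" without a cut, but it is a short summary, and 7.2.14 already states how the score is categorised.
- **That the cut is an error because no guideline is cited for it.** An exploratory model needs no such citation.

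**Conclusion.** The point holds as an inexpensive improvement to an exploratory analysis, not as a defect in the plan. Across the six assumed settings the cut loses about 23–42% of the information, or about 9–20 points of power at n = 500. The size rests wholly on assumption: the grade distribution, event share and effect size are not in the documents, proportional odds is taken as true, and the calculation is unadjusted although the planned model is multivariable. How the gain carries over after covariate adjustment and the 0.1 screen was not examined. The direction is less sensitive than the size: under proportional odds, every distribution tried favoured the ordinal model. No primary or secondary result is affected.

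Separately, SAP 8.2 and 8.3 say that no tests and no modelling will be done. That conflicts with 14.6 whichever outcome is used and needs its own correction.

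**What to change.** In SAP 14.6 and Table 53:
- Add a proportional-odds (cumulative-logit) model of the CFS grade with the same events and candidate factors.
- Fix a rule before the data are seen for merging sparse adjacent grades, for example 1–2 and 7–8.
- State a rule for grade 9, for example fitting the model with and without it.
- Report the common odds ratio with its 95% CI.
- Keep the >4 / ≤4 logistic model beside it, as the clinically labelled result and as a check of proportionality.

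The cost is some SAP wording and one extra model on data already collected. The downsides are an assumption to check and a common odds ratio that is less familiar than the odds of being frail.
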